11.1 Analysis Plan

The primary null hypothesis will be tested in an intent-to-treat analysis using a t-test, or nonparametric equivalent, of the between-group difference in means of the within-subject change in the post-transfusion RBC recovery from the initial study (under iron-deficient erythropoiesis conditions) and the subsequent study performed after randomization to iron repletion or placebo. A similar approach will be used to test the secondary objectives (i.e., the between-group difference in means of the within-subject change in fatigue score,³⁶ self-reported health and wellbeing score,³⁷ zinc protoporphyrin, hepcidin, soluble transferrin receptor, serum ferritin and hemoglobin concentration).

Furthermore, because we expect variable responses to iron repletion in the experimental group, and some crossover in the placebo group, we will also perform a secondary analysis to explore the effect of iron status on post-transfusion RBC recovery. We will use multiple regression to assess whether RBC zinc protoporphyrin level increases the R^2 of a model of post-transfusion recovery predicted by treatment group membership. We will examine pre-specified demographic variables (gender [male/female], race [white/not white], age [$<50/\geq 50$ years]) to see if we can identify one or more that may be effect modifiers. These factors will be considered for inclusion in an adjusted model. The specific criteria for inclusion are: (i) difference by treatment group significant at $\alpha = 0.10$ two-sided, and (ii) related to outcome at level $\alpha = 0.10$ two-sided. If any of the pre-specified covariates meet the criteria for inclusion, they will be incorporated in an adjusted model, and that model will become the primary analysis. Otherwise, the simple model will be primary. With 60 subjects, we will have 80% power to detect a partial correlation coefficient increase of 0.33 for the unique contribution of RBC zinc protoporphyrin level.⁴⁷

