1. Iron therapy will improve neurocognition and emotional well-being in donors with iron deficient erythropoiesis.
2. Metabolite levels in the transfusate will be associated with 24-hour post-transfusion RBC recovery and iron status.

Study Schema:

This is a randomized, controlled, double-blind clinical trial. 60 healthy regular donors who meet donation standards, while exhibiting iron-deficient erythropoiesis by laboratory test criteria, will donate a single standard RBC unit that will be leukoreduced and stored under standard conditions for 42 days. The FDA gold standard measure for the quality of RBCs destined for transfusion is the 51Cr-radiolabeled 24-hour RBC recovery study. Thus, a small aliquot of the transfused RBCs will be radiolabeled and injected into the volunteers on day 41 or 42 of storage. RBC recovery will be calculated from samples obtained at 5min, 7.5min, 10min, 12.5min, 15min, 30-minutes, 1-hour and 24 hours after autologous infusion as per the standardized protocol.⁴ For secondary outcomes, study surveys and neurocognitive assessments to assess symptoms of anemia and iron deficiency will also be performed prior to donation and prior to infusion.

In a prospective, randomized, double-blind manner, these donors will then receive either intravenous saline or low-molecular weight iron dextran (or ferric carboxymaltose if iron dextran is unavailable due to supply) within 1-day to 4-weeks after the first post-transfusion recovery study. After five months, they will donate a second RBC unit, similarly stored for 42 days, and autologous 51-chromium 24-hour post-transfusion RBC recoveries will again be determined. The primary outcome will be the group mean difference in 24-hour post-transfusion recovery difference from after treatment to baseline, between the groups receiving intravenous saline and iron.

[figure not shown]

TABLE OF CONTENTS

1. Background and Significance.....	7
2. Objectives	
2.1. Primary Hypothesis.....	11
2.2. Secondary Hypothesis.....	11
3. Study Population	
3.1. Enrollment Inclusion criteria.....	11
3.2. Enrollment Exclusion criteria.....	12
4. Trial Enrollment	
4.1. Screening / Recruitment.....	12
4.2. Randomization.....	13
4.3. Blinding.....	14
5. Interventions	
5.1. Blood donation.....	15
5.2. Chromium-51 post-transfusion RBC recovery	15
5.3. Total Dose Iron Infusion.....	16
5.4. Cognitive and Emotional Status Assessment.....	18
5.4.1. Cognition.....	18
5.4.2. Emotion.....	20
5.4.3. Hearing.....	20

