4.2 Randomization

Randomization will be performed using a computerized system with equal allocation (1:1) to iron repletion or placebo. Randomization will be stratified by gender; randomly permuted block sizes of 4, 6, or 8 will be used. The moment of randomization will be recorded and will occur only after successful completion of the first post-transfusion RBC recovery study (i.e., between Day #43-71; target is the day after the post-transfusion recovery study; performed on Harkness Pavilion 10). Volunteers will be admitted to the Columbia General Clinical Research Center (GCRC) (supported by the Columbia Clinical and Translational Science Award (CTSA)). One peripheral intravenous line will be inserted and blood (2 tubes, 10mL) will be drawn for determining the 24-hour post-transfusion recovery. The subject will be randomized at this point. The randomization scheme will be created by a statistician unaffiliated with the study team and provided to the research pharmacy and DSMB prior to study initiation. The CUMC research pharmacy will be responsible for randomizing each subject to the appropriate treatment arm and will prepare either the iron treatment or saline placebo and provide it to the study team in a blinded

fashion. If a subject arrives on the day of randomization and has a fever ($T>100.4F$) or feels ill, then the 24-hour post-transfusion recovery sample will be drawn, but randomization may be held until the subject feels better and reschedules.

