4.3 Blinding

The randomized group will only be known to the Columbia University Medical Center Research Pharmacy and the statistician who generated the randomization scheme. The study will be double-blind. As described in section 5.3, both a test dose of the iron treatment/placebo and the treatment/placebo will be blinded. The test dose will be administered prior to giving the full dose to ensure safety of treatment. A research pharmacist will provide the placebo (IV saline) or treatment (IV low molecular weight iron-dextran or ferric carboxymaltose) and test dose of iron/placebo in a tinted infusion bag and tubing specifically designed to maintain blinding in clinical research studies (Medipak). A research nurse unaffiliated with the study team, from the Outpatient or Inpatient Center at the Columbia General Clinical Research Center (Harkness Pavillion 10th Floor), will be responsible for the test infusion and total dose iron infusion. With this design, volunteers and study investigators will be blinded to whether volunteers receive the active intervention or placebo. Subjects in both groups will receive similar discharge instructions as if they had received low molecular weight iron-dextran (see Appendix 6 for discharge instructions). Only the research pharmacist and the statistician on the DSMB will not be blinded. Scheduling and logistic communications with volunteers will be made by the study coordinator, who will also be blinded to the treatment group. The research pharmacy will provide a standard 1-gram dose of low molecular weight iron-dextran, ferric carboxymaltose, or saline in special bags designed to conceal group assignment.

Situations may arise in which breaking the blind earlier would be in the best interest of the volunteer. In any situation in which a physician or the subject asks to be un-blinded to study treatment, a sealed copy of the randomization scheme for each subject will be kept in the investigator's office and will be broken upon request. Furthermore, the research pharmacy can be reached on an emergency basis to provide this information. Finally, any un-blinding that occurs will be reported to the DSMB and ultimately reported in the resulting publication.

5. Interventions

5.1 Blood Donation:

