10.1 Semi-Annual DSMB Reports

The DSMB will meet twice a year, either in-person or via teleconference. Reports will include:

- Baseline characteristics overall and by group
- Primary study endpoint overall and by group, (p-values to compare to early stopping boundary will only be provided after 20, 40, and 60 volunteers have been completed)
- Number, type, and severity of serious adverse events, overall and by treatment arm, with p-value for comparison of number of serious adverse events per group. This p-value will be compared to the p-value boundary from an alpha-spending approach approximating O'Brien-Fleming boundaries. No formal stopping rule is set for this comparison.
- Number, type, and severity of adverse events attributed as possibly, probably, definitely related to donation, iron or red cell infusion, overall and by treatment arm, with p-value for comparison of number of such adverse events per group. This p-value will be compared to the p-value boundary from an alpha-spending approach approximating O'Brien-Fleming boundaries. No formal stopping rule is set for this comparison.
- Proportion of subjects in each treatment arm with at least one serious adverse event possibly, probably, or definitely related to a donation, red cell or iron infusion, with p-value. This p-value will be compared to the p-value boundary from an alpha-spending approach approximating O'Brien-Fleming boundaries. No formal stopping rule is set for this comparison.
- Unexpected adverse events, and unanticipated problems overall and by treatment arm
- Site status

- Accrual
- Site/study compliance issues
- Data entry completeness and data QA

11. Statistical Considerations

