11.2 Sample Size Estimate

Based on preliminary data from our prior ^{51}Cr RBC recovery studies (IRB protocol #AAAI-0835), the standard deviation of the measure in our single site is 5.0%. Furthermore, the expected mean difference in post-transfusion RBC recovery

between iron replete mice and mice with iron-deficient erythropoiesis is 10.6%. If the difference were this large in humans, we would require <6 subjects (alpha = 0.05, two-sided, power = 0.80). However, we expect the difference to be less conspicuous in humans than in inbred mice. Thus, we power the study to detect a clinically relevant difference in post-transfusion recovery of 4%. Under this assumption, the calculated sample size required for each arm is 26 (alpha = 0.05, two-sided, power = 0.80). Furthermore, to allow for up to a 15% dropout rate (i.e., 4/26 subjects), we plan to randomize 30 subjects per arm for a total sample size of 60 subjects. Of note, randomization will occur after successful completion of the first post-transfusion recovery study; thus, we predict up to 70 individuals will need to be recruited.

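### The primary test uses baseline recovery only by subtraction; adjusting for it would gain power at almost no cost unless the follow-up-on-baseline slope is near 1, and section 11.2 does not say which SD its 5.0% is

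*Combined protocol and SAP*

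**What the plan says.** The Study Schema states: "The primary outcome will be the group mean difference in 24-hour post-transfusion recovery difference from after treatment to baseline", compared between saline and iron. Section 11.1 tests the "between-group difference in means of the within-subject change in the post-transfusion RBC recovery" by t-test or a nonparametric equivalent, by intention to treat. An adjusted model can become primary, but its only candidate covariates are gender, race and age. PTR1 is not among them.

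Section 4.2 says that randomization "will occur only after successful completion of the first post-transfusion RBC recovery study", so every randomized subject has a PTR1 value measured before treatment.

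Section 11.2 says, from earlier recovery studies, that "the standard deviation of the measure in our single site is 5.0"%. It takes 4 points as the difference to detect and obtains 26 per arm for 80% power at two-sided 0.05. Then, to allow for dropout, "we plan to randomize 30 subjects per arm". It gives no correlation between PTR1 and PTR2 and no separate SD for PTR2.

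**The concern.** Subtracting PTR1 is the best use of it only if a subject one point higher at baseline is, on average, one point higher at follow-up. If the slope is lower, subtraction over-corrects and adds baseline noise to the outcome. A 60-subject trial designed at about 80% power would then give up precision that it has already paid for.

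The unlabelled SD adds to this. For a change-score test, the calculation needs the SD of change. If 5.0% is the SD of one recovery, the stated power depends on a correlation that the plan never gives. Section 11.1 also expects variable responses to iron and some crossover among placebo subjects. The first could raise the PTR2 SD and the second could dilute the 4-point difference, so there is little margin to spare.

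**Working it through.** **Inputs from the plan.** Difference 4 points, SD 5.0, two-sided alpha 0.05, 26 per arm required, 30 per arm randomized (sections 11.1 and 11.2). **Assumed, because the plan does not give them:** rho and the PTR2 SD, shown as ranges.

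**1. The plan's own figure.** Noncentral t with SD 5.0 entered directly gives power 79.1% at 25 per arm, 80.7% at 26 and 86.1% at 30. The 26 per arm reproduces.

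**2. Formulas.** Let s1 and s2 be the SDs of PTR1 and PTR2, and slope = rho × s2/s1.
- Change-score variance: s1² + s2² − 2·rho·s1·s2, with 2n − 2 df.
- ANCOVA residual variance: s2²(1 − rho²), with 2n − 3 df and a small inflation for chance imbalance in PTR1.
- The first variance minus the second is s1²(1 − slope)². It is never negative and is zero only at slope 1.

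Example with s1 = s2 = 5 and rho = 0.5: the change variance is 25 + 25 − 25 = 25 and the ANCOVA variance is 25 × 0.75 = 18.75. The difference is 6.25 = 25 × (1 − 0.5)².

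**3. Reading A: 5.0 is the SD of one recovery (s1 = 5).** Power, change score → ANCOVA:

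| rho | s2 = 5, 26/arm | s2 = 5, 30/arm | s2 = 6, 26/arm |
|---|---|---|---|
| 0 | 52% → 80% | 58% → 86% | 44% → 65% |
| 0.3 | 67% → 83% | 73% → 89% | 58% → 69% |
| 0.4 | 73% → 86% | 79% → 91% | 64% → 72% |
| 0.5 | 81% → 90% | 86% → 94% | 72% → 77% |
| 0.7 | 95% → 97% | 98% → 99% | 90% → 90% |

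The 30-per-arm column assumes no dropout. With s2 = 5, the per-arm n for 80% power at these five values of rho is 51, 36, 31, 26 and 16 for the change score, and 27, 24, 23, 20 and 15 for ANCOVA. The change score reaches 80% only if rho is at least 0.49 (26 per arm) or 0.41 (30 per arm).

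**4. Reading B: 5.0 is the SD of change.** With equal SDs, s = 5/√(2(1 − rho)), so the ANCOVA residual SD is 5·√((1 + rho)/2): 4.03, 4.33 and 4.61 at rho 0.3, 0.5 and 0.7. At 26 per arm the change score has 80.7% throughout. ANCOVA has 93%, 90%, 86% and 82% at rho 0.3, 0.5, 0.7 and 0.9. If the PTR2 SD is 1.2 times the PTR1 SD, ANCOVA has 89%, 85% and 81% at rho 0.3, 0.5 and 0.7, and 80.0% at rho 0.8 (slope 0.96).

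**5. Downside.** When the slope is essentially 1, estimating it costs less than 1 point of power: 80.7% → 79.9% with residual SD 5.

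**6. Dilution.** With a 3.5-point difference (assumed), Reading A, s2 = 5, rho 0.5 and 26 per arm, power is 70% → 81%.

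**7. Interim looks.** Simulation with the Table 3 boundaries at 9, 17 and 26 per arm (Reading A, s2 = 5) gives 66.3% → 83.0% at rho 0.3 and 79.9% → 89.4% at rho 0.5. Type I error was 5.0–5.2% for both tests. Looks at 10, 20 and 30 per arm led to the same conclusion.

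**The case against.** The planned test is valid, matches the stated primary outcome and reproduces the stated sample size, so replacing it is an improvement rather than the repair of an error. That is correct, and it limits how serious the point is.

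The size of the gain rests on a correlation that the documents do not give. The largest gains need rho of 0.3 or less, and nothing in the plan supports a value that low. At rho 0.7 with equal SDs the gain is 2 points under Reading A and 5 under Reading B. It is already negligible at a slope of 0.84 (Reading A, s2 = 6, rho 0.7: 90.1% → 90.4%). This stands: the direction of the gain is secure, its size is not.

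There is a third possible reading, that 5.0% is a within-subject repeat SD. The change SD is then 5·√2 = 7.07 and power is 52%; ANCOVA reaches only about 63% at rho 0.5. It still gains but does not restore 80%, which makes labelling the SD more urgent.

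Section 11.1 expects variable response in the iron arm, not in both arms. With s2 = 6 in that arm only (s2 = 5 in the other, 26 per arm), simulation gives about 76% → 83% at rho 0.5 and 93% → 94% at rho 0.7, so the pattern is the same.

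Timing is the strongest practical objection. Semi-annual DSMB reports include "Primary study endpoint overall and by group", and the documents do not say whether such a report has been reviewed. The fix allows for this.

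**Conclusion.** The concern holds and should be fixed. PTR1 enters the primary test only by subtraction, and section 11.2 does not identify its SD. ANCOVA on PTR1 gains power under every reading of 5.0% unless the slope of PTR2 on PTR1 is close to 1, and costs less than 1 point there. For rho between 0.3 and 0.7 with equal SDs at 26 per arm, the gain is about 2 to 17 points under Reading A and 5 to 13 under Reading B. These sizes rest on assumed values of rho and the PTR2 SD.

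The planned test is not invalid, and the trial is not shown to be underpowered. The stated 80% holds if 5.0% is the SD of change, or if it is a single-measurement SD with equal SDs and rho of about 0.49 or more.

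**What to change.** - **Section 11.1.** Make the primary analysis an ANCOVA with PTR2 as outcome, treatment as factor and PTR1 as covariate. The treatment coefficient estimates the same between-group difference. Keep PTR1 in any model that adds gender, race or age. Make the nonparametric fallback a rank-based analysis that includes PTR1, and name the method and what triggers it. Because the secondary objectives follow a similar approach, say whether they too are baseline-adjusted.
- **Sections 10.1 and 11.3.** Use the same model for the DSMB p-values and interim Z-scores.
- **Section 11.2.** State which SD 5.0% is. Restate power at 26 and 30 per arm for the chosen analysis, with the assumed rho and PTR2 SD and their source.
- **Timing.** Settle this before any unblinded comparison of the primary endpoint is reviewed. If one has been reviewed, either the blinded team decides without DSMB input (section 4.3 says that "volunteers and study investigators will be blinded to whether volunteers receive the active intervention or placebo"), or the change-score test stays primary and ANCOVA is named as a sensitivity analysis. Clarifying the SD is worthwhile in either case.

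**Cost.** If no by-group comparison has been reviewed, this means text edits to four sections, with no extra subjects, visits or data. After such a review it is more than a text edit. The statistical cost is one residual degree of freedom.

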2.2 Secondary Hypothesis

- 1) The extent of iron-deficient erythropoiesis, as measured by RBC zinc protoporphyrin levels, will predict the 24-hour post-transfusion RBC recovery.
- 2) There will be a good correlation ($R^2 > 0.5$) between RBC zinc protoporphyrin levels and other markers of iron status: ferritin, hepcidin, soluble transferrin receptor, reticulocyte hemoglobin.
- 3) Iron repletion will improve fatigue score³⁶ and self-reported health and wellbeing score.³⁷
- 4) Iron repletion will decrease RBC zinc protoporphyrin and soluble transferrin receptor levels.
- 5) Iron repletion will increase hepcidin, ferritin, and hemoglobin levels.
- 6) Iron repletion will improve the following neurocognitive scores:
 - a) Cognitive Function Composite Score
 - b) Executive Function
 - c) Attention
 - d) Episodic Memory
 - e) Language
 - f) Processing Speed
 - g) Working Memory
- 7) Iron repletion will improve the following emotional well-being scores:
 - a) quality of life
 - b) fatigue
 - c) depression
 - d) anxiety
- 8) Metabolite levels in the RBC unit will correlate with iron status and 24-hour post-transfusion RBC recovery.

3. Study Population

3.1 Enrollment Inclusion Criteria:

- 1) 18-75 years old;
- 2) healthy (by self report);

- 3) body weight >110 lbs;
- 4) female hematocrit >38%, male hematocrit >39%;
- 5) frequent blood donor (men ≥ 2 and female ≥ 1 RBC unit donations in past year);
- 6) ferritin <15 ng/mL;
- 7) zinc protoporphyrin >60 μ mol/mol heme.

3.2 Enrollment Exclusion Criteria:

- 1) ineligible for donation based on the New York Blood Center donor autologous questionnaire;
- 2) C-reactive protein >10 mg/L;
- 3) sickle cell trait (by self report);
- 4) systolic blood pressure >180 or <90 mm Hg, diastolic blood pressure >100 or <50 mm Hg;
- 5) heart rate <50 or >100;
- 6) temperature >99.5°F prior to donation (attempts will be made to reschedule donation if possible);
- 7) temperature >100.4°F or subjective feeling of illness prior to ^{51}Cr 24-hour RBC recovery study (to avoid the subject having a concurrent illness that may affect post-transfusion recovery); (attempts will be made to reschedule donation and ^{51}Cr 24-hour RBC recovery study);
- 8) positive results on standard blood donor infectious disease testing;
- 9) pregnancy;
- 10) taking, or planning to take, iron supplements and not willing to stop for duration of study;

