4.1 Screening/Recruitment

The New York Blood Center study staff will send a recruitment letter/email (see Appendix 1) to potential subjects who are 18-75 years old and frequent blood donors donating in the Manhattan catchment area. We will define frequent blood donors as (1): men who have donated the equivalent of at least 2, and women who have donated the equivalent of at least 1, RBC units in the past year.

Volunteers responding to the recruitment email will be screened for participation in the study by phone or email (see Appendix 7 for all screening forms) and then invited for a

screening meeting (P&S 14-434) to confirm eligibility and provide informed consent.

Screening day (P&S 14-434): All volunteers will be given the health questionnaire they would receive upon donation at the New York Blood Center (see Appendix 7). All volunteers who decide to proceed with screening and sign consent will have four tubes of blood drawn to determine baseline laboratory values and to perform a blood type and antibody screen. If the baseline hematocrit is >38% (female) or >39% (male), ferritin < 15ng/mL, zinc protoporphyrin level is > 60 umol/mol heme, and C-reactive protein is <10mg/L (see inclusion/exclusion criteria above) then the volunteer will be scheduled for an autologous whole blood donation at the New York Blood Center, and scheduled for an autologous 51-Chromium red cell recovery study 6 weeks after donation. At that time, neurocognitive assessments and emotional wellbeing will be performed as well (see Appendix 2-5 for surveys and section 5.4). Re-screening: Those subjects who meet the ferritin <15ng/mL and the zinc protoporphyrin > 60umol/mol heme criteria, but do not qualify due to a low hematocrit may be re-screened between 2 weeks to 3 months later.

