6.1 Summary Timeline

The schedule of measurements is summarized in **Table 1**. Following successful screening and signed informed consent, subjects will donate a unit of autologous red blood cells (Donation1). This will be followed 40-42 days later by the baseline 51-Chromium post-transfusion recovery study. Following the 24-hour post-chromium infusion blood draw, the subjects will be randomized to iron infusion or placebo (Iron infusion1). Five months \pm 4 weeks later, subjects will donate the second unit of autologous blood (Donation2). The second 51-Chromium post-transfusion recovery study will be performed 40-42 days after this donation. Subjects will have to return 24-hours after chromium infusion to determine the 24-hour post-transfusion recovery. Surveys and neurocognitive assessments will be conducted prior to Donation1, PTR1, Donation2, and PTR2.

Because an active type and screen must be obtained before the blood bank issues the stored RBC unit and the radioactive 51-Cr-labeling can occur, we will provide subjects with the option of coming in up to 30 days prior to the scheduled PTR study to obtain a type and screen sample (1 tube of blood by standard venipuncture). This will provide for a shorter day for the PTR study because there will no longer be the need to wait for the type and screen testing and the study can begin once the subject arrives. If a subject chooses not to provide this optional blood draw, a blood sample will be taken when the IV lines are placed for the PTR study and the PTR study will proceed after the blood bank issues the blood and it is radiolabeled per hospital guidelines.

Table 1: Schedule of Measurements

Day of study	Urine pregnancy test	CBC with reticulocyte count	Iron parameters*	C-reactive protein	Type and Screen	51-Cr PTR**	Iron/Placebo infusion	Surveys/Neuro-cognitive	Metabolomics****
Screening		X	X	X	X				
Donation1	X	X	X	X				X	X
Blood draw (optional)***					X				
PTR1 (40-42 days after Donation1)	X	X	X	X	X	X		X	
Iron infusion1 (1 day after PTR1)	X						X		
Donation2 (5months ± 4 weeks after iron infusion1)	X	X	X	X				X	X
Blood Draw (optional)***					X				
PTR2 (40-42 days after Donation2)	X	X	X	X	X	X		X	
Final blood draw (1 day after PTR2)						X – collection of 24 hour (+/- 4hr) time point for final measurement			

*Iron parameters = Zinc Protoporphyrin (ZPP), iron, total iron binding capacity (TIBC), transferrin saturation, ferritin, soluble transferrin receptor, hepcidin.

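### The secondary outcomes are measured at least twice before and twice after treatment, but section 11.1 tests one within-subject change, names no visits, and leaves some scores off its list

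*Combined protocol and SAP*

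**What the plan says.** All references are to the combined protocol and SAP.

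- **Section 11.1** tests the primary outcome by comparing the arms on change in recovery from the first recovery study to the second. It then says: "A similar approach will be used to test the secondary objectives". The bracketed list that follows has seven outcomes: fatigue, self-reported wellbeing, and "zinc protoporphyrin, hepcidin, soluble transferrin receptor, serum ferritin and hemoglobin concentration". It gives no baseline visit, post-treatment visit, averaging rule or repeated-measures model for them.
- **Section 6.1** sets the timing of the patient-reported and cognitive outcomes: "Surveys and neurocognitive assessments will be conducted prior to Donation1, PTR1, Donation2, and PTR2".
- **Table 1** marks the blood count and the iron parameters at those four visits and also at Screening. Its footnote reads "Iron parameters = Zinc Protoporphyrin (ZPP), iron, total iron binding capacity (TIBC), transferrin saturation, ferritin, soluble transferrin receptor, hepcidin".
- **Treatment** falls between PTR1 and Donation2: "Following the 24-hour post-chromium infusion blood draw, the subjects will be randomized to iron infusion or placebo (Iron infusion1"). Donation2 follows the infusion by five months ± 4 weeks.
- **Baseline** is used in two senses. In section 4.1 volunteers at screening "will have four tubes of blood drawn to determine baseline laboratory values". In section 6.1 the word belongs to PTR1: "This will be followed 40-42 days later by the baseline 51-Chromium post-transfusion recovery study".
- **Section 2.2**, hypothesis 6, begins "Iron repletion will improve the following neurocognitive scores" and lists a composite and six domain scores. Hypothesis 7 adds depression and anxiety. None of these is in the section 11.1 list.

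**The concern.** The change-score t-test fits an outcome with one value on each side of treatment. Applied to outcomes with several values on each side, it leaves two matters open.

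The first is efficiency. A single change leaves two or three of the collected values out of the comparison, and a raw change score does not use the baseline as well as covariate adjustment does. The trial is sized for recovery only; section 11.2 gives no power for between-group comparisons of these outcomes.

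The second is freedom of choice. With no visits named, the pair can be settled after data are seen. The pairs are not interchangeable: Donation visits come before a study phlebotomy and PTR visits come 40-42 days after one. Donation1 to Donation2 and PTR1 to PTR2 are matched on time since study donation; the cross pairs are not. This could matter for hemoglobin, ferritin and fatigue.

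For cognition, depression and anxiety the gap is wider, since section 11.1 assigns them no explicit test.

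**Working it through.** **1. The plan's own figure.** Section 11.2 uses a difference of 4, SD 5.0, two-sided alpha 0.05 and power 0.80. The standardised difference is 4/5 = 0.8. A two-sample t-test needs 25.5, so 26 per arm, as stated. I use 26 per arm below.

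**2. Count of values and pairs.**
- Surveys and cognition: 2 before × 2 after = 4 pairs; one change uses 2 of 4 values.
- Iron markers and hemoglobin: 3 before (Screening, Donation1, PTR1) × 2 after = 6 pairs; one change uses 2 of 5 values.

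**3. Precision.** The documents give no correlations, so these are assumptions: w between two values in the same period, b between values in different periods, equal variances set to 1. Screening is left out.
- Single-pair change: variance 2(1 − b).
- Mean post minus mean pre: variance 1 + w − 2b.
- ANCOVA of mean post on mean pre: with m = (1 + w)/2, residual variance m − b²/m.
- ANCOVA on one pair: residual variance 1 − b².

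Example, w = 0.9 and b = 0.7. Single change: 2 × 0.3 = 0.60. Mean change: 1.9 − 1.4 = 0.50, SE ratio √(0.50/0.60) = 0.913. ANCOVA on means: 0.95 − 0.49/0.95 = 0.434, SE ratio √(0.434/0.60) = 0.851.

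**4. Selection of a pair.** Simulated with no treatment effect, 26 per arm, two-sided 0.05, at least 20,000 trials per setting. The rate is the chance that at least one available pair gives p < 0.05.

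| w / b | SE ratio, mean change | SE ratio, ANCOVA on means | Best of two matched pairs | Best of four pairs |
|---|---|---|---|---|
| 0.5 / 0.5 | 0.707 | 0.645 | 10% | 16% |
| 0.7 / 0.5 | 0.837 | 0.746 | 9% | 14% |
| 0.7 / 0.7 | 0.707 | 0.675 | 10% | 16% |
| 0.8 / 0.6 | 0.866 | 0.791 | 9% | 13% |
| 0.9 / 0.7 | 0.913 | 0.851 | 9% | 11% |
| 0.9 / 0.5 | 0.949 | 0.829 | 8% | 10% |

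The SE falls by 5-29% with the mean change and by 15-35% with ANCOVA on the means. ANCOVA on a single pair has SE ratio √((1 + b)/2), which is 0.866 at b = 0.5 and 0.922 at b = 0.7, a fall of 8-13%. For the iron markers, picking the best of six pairs gives about 12-23%.

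**5. What averaging can cost.** Take an effect that a single-pair change t-test detects with 81% power at one post-treatment visit, and suppose the effect is half as large at the other. The averaged effect is then 0.75 of the larger one. Power of the mean-change test becomes 85% at 0.7/0.7, 74% at 0.8/0.7 and 64% at 0.9/0.7. ANCOVA on the means gives 88%, 79% and 70% in the same settings.

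**The case against.** **A default reading exists.** Since the primary compares the first recovery study with the second, PTR1 to PTR2 is a plausible meaning for the secondary outcomes too. This has force, but the text does not say so, and it calls both the screening laboratory values and PTR1 baseline. A named pair would remove the selection problem; it would not recover the unused values.

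**The sizes depend on unknown correlations.** This stands. A reader might infer that half the information is thrown away. For surveys and cognition half is a count of values; the variance of the change halves only if visits about six weeks apart correlate no better than visits across the treatment period. Likewise 16% belongs to equal correlations and to an analyst willing to use mismatched pairs. Nothing in the documents shows an intention to choose a pair from the data.

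**The list in section 11.1 is limited.** A reader might infer that the plan applies the change t-test to cognition. The seven listed outcomes do not include it, so the better description is that no test is named for hypothesis 6 or for depression and anxiety.

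**Averaging changes the question.** Donation2 reflects status about five months after infusion; PTR2 reflects it after a further unit has been removed. The average is a slightly different estimand, and step 5 shows it can lose power if the effects differ much. This stands and is a real cost. It does not rescue the raw change score, because covariate adjustment gains 8-13% in SE even on one pair.

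**Only secondary outcomes are touched, and one pre-named change t-test is valid.** Both are true and limit the importance of the point.

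**Conclusion.** The concern holds for the secondary outcomes. The plan specifies a single change without visits for outcomes that have four or five values, and omits cognition, depression and anxiety from its list. A baseline-adjusted analysis of both post-treatment visits is more precise than a single-pair change t-test: about 15-35% in SE, on assumed correlations of 0.5-0.9 within and 0.5-0.7 across periods, equal variances and a similar effect at Donation2 and PTR2. The false-positive rates of 8-10% and 10-16% are conditional: they apply only if the pair is chosen after seeing results. The primary outcome has one value on each side and is not affected. The change should be made, but the trial's main conclusion does not depend on it.

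**What to change.** Amend section 11.1 as follows.

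1. List every between-group secondary outcome: SF-36, fatigue, BDI-II, BAI, the cognitive composite and six domain scores, zinc protoporphyrin, ferritin, hepcidin, soluble transferrin receptor and hemoglobin.
2. For each, replace the change t-test with a baseline-adjusted mixed model (or ANCOVA) with Donation2 and PTR2 as outcomes, adjusted for the Donation1 and PTR1 values and for sex, the randomization stratum.
3. State that Screening ferritin and zinc protoporphyrin are not used as baseline. They decided entry, so they are prone to regression to the mean; that affects both arms alike but adds noise.
4. Report the average treatment effect as the main estimate, with the visit-specific effects (Donation2 against Donation1, PTR2 against PTR1) alongside.

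This needs SAP wording only and no new data, and it should be settled before unblinding. A mixed model also keeps a subject who misses one post-treatment visit. The cost is the slightly different estimand and the possible loss of power if the effect is much smaller at one post-treatment visit; the visit-specific estimates make that visible. If the sponsor prefers a single matched pair, naming it per outcome and adjusting for its baseline would still close the choice and keep part of the gain.
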